	11.1 Participating Centers	
	11.2 Clinical Trial Supplies	
	11.3 Investigator Site File	
	11.4 Final Report	
	11.5 Retention of Study Records	
	11.6 Confidentiality and Publication	
12.0	REFERENCES	59
13.0	APPENDICES	61

GLOSSARY

Abbreviation/Term Definition

β-hCG Beta-human chorionic gonadotrophin

μg Microgram

ABQOL Autoimmune Bullous Disease Quality of Life

AE Adverse event

ASI Application Setup Instructions
BMZ Basement Membrane Zone

BP Bullous Pemphigoid

BPDAI Bullous Pemphigoid Disease Area Index

CDM Clinical Data Management / Manager

CDMoP Clinical Data Monitoring Plan

CFR Code of Federal Regulations

cGMP Current Good Manufacturing Practice

CMV Cytomegalovirus

CRF Case report form (also eCRF for electronic CRF)

CRO Contract research organization

CSR Clinical Study Report
CV% Coefficient of variance
DIF Direct Immunofluorescence

Direct inimunoridorescen

DM Data Management
DVP Data Validation Plan

ECG Electrocardiogram

EDC Electronic Data Capture

FDA Food and Drug Administration

GCP Good Clinical Practice

HIV Human immunodeficiency virus

HPF High Power Field

ICF Informed consent form

ICH International Conference on Harmonisation

IEC Independent Ethics Committee

IF Immunofluorescence IgG Immunoglobulin G

IRB Institutional Review Board

Abbreviation/Term Definition

IV Intravenous kg Kilogram

MedDRA® Medical Dictionary for Regulatory Activities

mg Milligram
mL Milliliter
mM Millimolar

MOH Ministry of Health

PBMC Peripheral Blood Mononuclear Cell

PBS Phosphate buffered saline

PD Pharmacodynamic
PK Pharmacokinetic

PPD Purified Protein Derivative

QA Quality Assurance
QOL Quality of life

SAE Serious adverse event

SOP Standard operating procedure

SUSAR Suspected unexpected serious adverse reaction

TB Tuberculosis

WHO World Health Organization

1.0 INTRODUCTION

1.1 BULLOUS PEMPHIGOID

Bullous pemphigoid (BP) is an inflammatory, autoimmune blistering disease of the skin that mainly affects people over 60 years of age. The overall incidence is increasing in Europe and the US with an incidence rate between 20-30 new cases per million inhabitants per year and an incidence rate up to 350 new cases per million inhabitants per year among the population aged 80 years and older [4, 5]. To date, the only effective treatment for BP is high dose steroids, which are associated with side effects such as increased morbidity risk, particularly in the elderly population. It is therefore necessary to develop a safe, efficacious treatment for this rare disease and/or treatment which will enable steroid tapering.

BP is characterized by deposits of IgG antibodies and/or complement component 3 (C3) along the epidermal basement membrane zone (BMZ) [6, 7, 8]. Following antibody binding to hemidesmosomal antigens (BP180 and BP230) in the BMZ, complement activation occurs and inflammatory cells infiltrate the subepidermis causing tense blisters to form mainly on the flexor surfaces of arms and legs, axillae, groin, and abdomen. The blisters of BP are filled with a clear fluid, which tend to develop on the edge of erythematous plaques and may be widespread or local, and intense itching is common [9].

High dose oral corticosteroids (prednisone, 1 mg/kg/day) have been considered the mainstay of treatment for many years. It has been clearly demonstrated that these high doses are deleterious and directly responsible for a high rate of treatment side effects and a high mortality rate [3, 10, 11]. Super potent topical corticosteroids have been demonstrated to be more effective and safer than high dose oral corticosteroids, reducing the frequency of steroid-related side effects and mortality rate, while controlling BP lesions in between 95% to 100% of patients in two randomized controlled studies of more than 700 patients [3, 12]. Despite their high efficacy, topical corticosteroids are often considered inconvenient, necessitating the assistance of relatives or a nurse to apply the cream on the whole body surface for extended periods of time and their use is associated with poor compliance in an elderly population [18].

Immunosuppressants are poorly tolerated in elderly BP patients. Randomized controlled studies have failed to demonstrate a corticosteroid sparing effect, but revealed a higher rate of treatment side effects in patients receiving combined treatment compared with those treated with corticosteroid alone.

Antibiotics (tetracycline, dapsone) are considered safer than oral corticosteroids. However, their efficacy is controversial and has not been clearly demonstrated.

In summary, although BP lesions can be adequately and rapidly controlled with either oral or topical corticosteroids, due to significant associated side effects and poor compliance with use of steroid creams over large body surface areas, there is a significant need for novel, efficacious treatments.

1.1.1 The Role of Eotaxin and Eosinophils in Bullous Pemphigoid

Eotaxin-1 is an eosinophil-selective chemokine produced by a variety of cell types including eosinophils, epithelial cells, fibroblasts, endothelial cells, T-lymphocytes, monocytes and macrophages following induction by pro-inflammatory mediators [13]. Eotaxin is known to play

a significant role in the tissue accumulation of eosinophils that accompanies allergic inflammation. While eosinophils are an important component of innate immunity, the accumulation of eosinophils in tissues can be detrimental. Eosinophil degranulation products have significant cytotoxic effects on tissues, and cytokines known to be released by eosinophils enhance inflammatory signaling.

The cellular infiltrate that characterizes BP is comprised mainly of eosinophils, but also includes mast cells and lymphocytes. High levels of Th2 cytokines are found in BP tissue and blister fluid. Eosinophil infiltration and Th2-associated chemokines play a key role in the pathogenesis of BP [14]. The presence of eosinophils in BP skin lesions is well documented, and the chemotactic factors responsible for eosinophil recruitment into the tissue have been identified.

Immunoreactivity to eotaxin, localized to the epidermis and eosinophil granules, has been found in tissue biopsies from BP patients and in blister fluid [7, 14-16], consistent with increased chemotaxis of Th2 cells toward the blister fluid. Eotaxin and interleukin (IL-5), another Th2 cytokine, cooperate to activate and recruit eosinophils, ultimately contributing to the tissue damage characteristic of BP [15].

Compared to suction blister fluids obtained experimentally in healthy individuals, blister fluids from BP patients contain significantly higher amounts of eotaxin-1 [17], indicating substantial production of eotaxin-1 at sites of tissue damage and suggesting that eotaxin-1 is responsible for chemotaxis of both eosinophils and Th2 cells. From early stages of the disease via local production and release of cytokines (such as IL-4, IL-5) and eotaxin-1 itself, the immunological processes underlying blister formation are amplified and maintained [7].

These studies provide strong rationale for the use of therapeutic agents targeting eosinophils and molecules that regulate eosinophil function such as eotaxin-1 in the treatment of BP.

1.2 INVESTIGATIONAL THERAPY

Bertilimumab is a human monoclonal IgG₄ antibody that neutralizes human eotaxin-1 and inhibits its function. The product is manufactured in a mammalian cell line engineered using recombinant DNA technology to produce the antibody.

1.2.1 Nonclinical Studies

A single-dose toxicity study with bertilimumab was conducted in Rhesus monkeys (6 per dose group). Monkeys were administered a single IV infusion of bertilimumab at a dose of 10 or 100 mg/kg and observed for 28 and 7 days, respectively. No effects on morbidity or mortality were observed. Body weights and food consumption were not impacted by bertilimumab treatment and all clinical chemistry and hematological parameters examined were unaffected. In a repeat-dose toxicity study, Rhesus monkeys (6 per dose group) were administered 10, 30 or 100 mg/kg bertilimumab twice weekly by IV infusion for 28 days. There were no deaths or significant morbidity following treatment with bertilimumab. No effects on clinical chemistry, ophthalmoscopic or hematological parameters or body weight were observed. At sacrifice (end of study period), there were no treatment-related changes in organ weight or macroscopic/microscopic observations.

For detailed information on pre-clinical studies, please refer to the Investigator's Brochure.

1.2.2 Clinical Studies

Three clinical studies of bertilimumab were conducted in Europe: a Phase 1 study in healthy volunteers (study CAT-213-0101), and Phase 2 studies in patients with allergic rhinitis and allergic conjunctivitis (studies CAT-213-0103 and CAT-213-0203, respectively). Ninety nine (99) individuals have received bertilimumab: 45 via the IV (45/99, 45%), eight (8) via the intranasal (8/99, 8%), and 46 via the topical ocular (46/99, 46%) routes of administration. Thirteen individuals received IV bertilimumab at doses ≥500 mg (maximum dose administered: 770 mg). In these studies, bertilimumab was well tolerated and no dose-related adverse events (AEs) were noted. To date, no clinical studies of bertilimumab have been conducted in patients with BP.

For additional information on these clinical studies, please refer to the Investigator's Brochure.

1.3 STUDY RATIONALE

Bertilimumab is the first monoclonal antibody to specifically neutralize human eotaxin-1. Bertilimumab has been shown to inhibit eotaxin-stimulated migration of cells and may therefore be useful in the treatment of human diseases such as BP, where eosinophil accumulation is an important feature.

This study will provide both safety and efficacy data for internal decision-making regarding further development of bertilimumab in BP. A positive proof of concept in this study would be supportive of further development via randomized control trial(s) to demonstrate that bertilimumab is an adequate candidate for maintenance therapy in newly diagnosed patients and patients resistant to corticosteroid tapering with moderate to extensive BP. Its efficacy in newly diagnosed patients would be proven by allowing reduced initial doses of corticosteroids and reduced cumulative dose of corticosteroids by facilitating rapid tapering to 10 mg prednisone equivalent or lower after initial control of BP lesions. Its efficacy in patients resistant to corticosteroid tapering would be proven by allowing patients to be tapered down from corticosteroids without flaring and/or allowing smaller doses of oral corticosteroids to control the disease.

The study will investigate newly diagnosed adult patients and adult patients resistant to corticosteroid tapering with moderate to extensive BP. The treatment period will include three IV infusions of 10 mg/kg bertilimumab on study Days 0, 14 (±2 days) and 28 (±2 days) and a follow-up period up to Day 84 (or Day 118 for males who have had abnormal semen analysis results on Day 0, Day 14 or Day 28) relative to pre-dose Visit 2. Patients will receive concomitant oral steroids during the treatment and follow-up period.

It has been demonstrated that relatively low doses of corticosteroids (e.g., 30 mg/day) are only partially effective in achieving disease control or complete remission. The rapid onset of steroid action is desired in order to alleviate patient symptoms as quickly as possible while the slower acting biologic takes effect. A key focus in this treatment is the goal is to taper the steroids as rapidly as possible, a difficult feat to achieve with steroids in isolation. Initial treatment with prednisone has therefore been added to bertilimumab treatment. This study is designed to demonstrate that the successful tapering of corticosteroids over a shorter period of time than physicians have been accustomed to will be possible with the administration of bertilimumab, thereby mitigating risks associated with long term steroid use.

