2.2 STUDY ENDPOINTS AND OUTCOMES

Primary Endpoints

Safety Endpoints

Safety will be evaluated on the basis of the following parameters:

- Adverse events (AE)
- Infusion reactions
- Injection site reactions
- Physical examination
- Vital signs (blood pressure, heart rate, temperature)
- ECG
- Concomitant medications
- Laboratory evaluation (hematology, biochemistry, anti-bertilimumab antibodies)

Secondary Endpoints

Efficacy Endpoints

- Proportion of patients who achieve a reduction in the Total Activity Score of the BPDAI score of at least 50%, 75% and 90% at visits 5 (Day 42), 6 (Day 56), 7 (Day 70), or 8 (Day 84) compared to:
 - Screening, if patient is resistant to corticosteroid tapering
 - Visit 2 (Day 0), if patient is newly diagnosed.
- Proportion of patients who have tapered to prednisone dose of ≤10 mg/day at Visit 8 (Day 84) and/or 2 and 4 months after Visit 8 (Day 84)
- Proportion of patients who achieve control of disease activity at Visits 5 (Day 42), 6 (Day 56), 7 (Day 70), or 8 (Day 84)
 - Ocurrol of disease activity is defined as the time when at least two of the following occur: new lesions cease to form, established lesions begin to heal and/or pruritic symptoms start to abate. Control of disease activity will be assessed by the BPDAI and the investigator's assessment of lesion healing.
- Mean time to control of disease activity from:
 - Screening, if patient is resistant to corticosteroid tapering
 - Visit 2 (Day 0), if patient is newly diagnosed
- Change in BPDAI score at each scheduled measurement timepoint compared to:
 - Screening, if patient is resistant to corticosteroid tapering
 - Visit 2 (Day 0), if patient is newly diagnosed
- Change in BPDAI pruritis component (Visual Analogue Scale) at each scheduled measurement timepoint compared to:

- Screening, if patient is resistant to corticosteroid tapering
- Visit 2 (Day 0), if patient is newly diagnosed
- Change in ABQOL score at each scheduled measurement timepoint compared to:
 - Screening, if patient is resistant to corticosteroid tapering
 - Visit 2 (Day 0), if patient is newly diagnosed

Pharmacokinetic (PK) Endpoints

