6.8.1 Concomitant Corticosteroid Therapy

• Newly diagnosed patients:

Due to the potential effects of long-term and/or high-dose systemic corticosteroid usage on bullous pemphigoid, patients will be permitted to take systemic oral corticosteroids specifically for bullous pemphigoid only for a period of 4 weeks prior to the first treatment administration (Visit 2 - Day 0) at doses no greater than 40 mg/day prednisone equivalent.

Patients who have taken systemic oral corticosteroid for bullous pemphigoid longer than 4 weeks prior to the first treatment administration (Visit 2 - Day 0) or at doses greater than 40 mg/day prednisone equivalent at any time are excluded from the study.

For patients who have used systemic corticosteroids for reasons other than bullous pemphigoid, a washout period of 4 weeks prior to the first treatment administration (Visit 2 - Day 0) is required.

For patients who are taking systemic oral corticosteroids at a daily dose between 40 mg/day and 30 mg/day prednisone equivalent for BP within 4 weeks prior to the first treatment administration (Visit 2 - Day 0), tapering of systemic corticosteroids is to be conducted at the discretion of the investigator. However, patients must be on 30 mg/day prednisone equivalent for the first treatment administration (Visit 2 - Day 0). For patients who are taking less than 30 mg/day prednisone equivalent prior to the first administration day (Visit 2 - Day 0), a stable dose of systemic corticosteroids should be maintained until Visit 2 (Day 0).

Patients resistant to corticosteroid tapering:

No wash-out period is required.

The tapering schedule depicted in Table 1 is recommended for the remainder of the study.

Table 1: Recommended Corticosteroid Tapering Regimen

Systemic corticosteroid dose (prednisone equivalent) per day	Tapering schedule
≥30.0-10.1 mg/day	Decrease by 5 mg each week
$10.0-0~\mathrm{mg/day}$	Decrease by 2.5 mg each week

Corticosteroid management can occur either during a scheduled visit, unscheduled visit, or phonecall follow-up per the investigator's discretion.

Table 2: Corticosteroid Comparison Chart

	Approximate Equivalent Dose, mg	Relative Potency
Cortisol	20	1.0
Cortisone	25	0.8
Prednisone	5	4.0
Prednisolone	5	4.0
Triamcinolone	4	5.0
Dexamethasone	0.75	30-150

Reference: Welsh GA, Manzullo EF and Nieman LK The surgical patient taking glucocorticoids. 2007 UpToDate® www.uptodate.com.

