### 1 Introduction

### 1.1 General

Bertilimumab is the first monoclonal antibody to specifically neutralize human eotaxin-1 (eotaxin). Bertilimumab has been shown to inhibit eotaxin-stimulated migration of cells and may therefore be useful in the treatment of human diseases such as Bullous Pemphigoid (BP), where eosinophil accumulation is an important feature.

The purpose of this study is to provide proof of concept for the treatment of BP with bertilimumab. This study will provide both safety and efficacy data for internal decision-making regarding further development of bertilimumab in BP. Its efficacy in newly diagnosed patients would be proven by allowing reduced initial doses of corticosteroids and a reduced cumulative dose of corticosteroids by facilitating rapid tapering to 10 mg prednisone equivalent or lower after initial control of BP lesions. Its efficacy in patients resistant to corticosteroid tapering would be proven by allowing patients to be tapered down from corticosteroids without flaring and/or allowing smaller doses of oral corticosteroids to control the disease.

The study will investigate newly diagnosed adult patients and adult patients resistant to corticosteroid tapering with moderate to extensive BP. The treatment period will include three IV infusions of 10 mg/kg bertilimumab on study Days 0, 14 (±2 days) and 28 (±2 days) and a follow-up period up to Day 84 (or Day 118 for males who have had abnormal semen analysis results on Day 0, Day 14 or Day 28) relative to pre-dose Visit 2. Patients will receive concomitant oral steroids during the treatment and follow-up period.

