### **Prednisone Dose**

All prednisone doses are summarized in either the Concomitant Medications form or the Corticosteroid Therapy Form depending on the protocol version used. Note that modification of prednisone doses at any time during the study was acceptable.

Therefore, both the mean dose throughout the trial and the cumulative dose will be of interest.

The following prednisone dose summaries will be provided:

- 1. For each patient, divide the relevant form records into the periods which are consistent with the study periods:
  - a. Prednisone dose at Visit 2 will be based on all records done between the Visit 2 (including) and Visit 3 (not including). A single (long) record could be split into several records to fit the trial periods. For example, if a record starts before Visit 2 and ends before Visit 3, only the relative part from Visit 2 date onwards will be related to Visit 2.
  - b. Similarly, all other trial visits will be defined, up to Visit 8.
- 2. For each patient and each trial period, calculate the total prednisone dose (mg) taken during this period. Frequency and the length of exposure should be considered in this calculation. (For example, Dose\*Frequency\*Number of Days)

- 3. The mean prednisone dose (mg/day) for each period will be calculated as the total dose in the previous step divided by the period duration (days).
- 4. The cumulative prednisone dose (mg) for each period will be calculated as the sum of the total prednisone dose (mg) over all preceding periods, starting at Visit 2.
- 5. Calculations similar to those described in steps (3) and (4) will be repeated, but with dose adjusted for a patient's weight. The mean weight adjusted prednisone dose (mg/kg/day) for each period will be calculated as the total dose in step (2) divided by the period duration (days) and divided by the subject's weight (kg) obtained at this visit (or the most recent available). The cumulative weight adjusted prednisone dose (mg/kg) for each period will be calculated as the cumulative sum over weight adjusted doses over all preceding visits.
- Reduction (measured continuously) in prednisone mean dose (mg/day) from Visit 2
   (Day 0) to each subsequent visit
- Dichotomous reduction in prednisone mean dose (mg/day) will be defined as
  - O Success "1", if the dose at Visit 8 (Day 84) does not exceed 10 mg/day
  - o Failure "0", otherwise

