#### Prednisone dose

- Descriptive statistics of prednisone doses (mean dose, weight adjusted mean dose, cumulative dose and weight adjusted cumulative dose) will be presented by visit.
- Descriptive statistics of reduction in mean dose and weight adjusted mean dose will be presented by visit.
- Frequency distribution of dichotomous reduction in mean dose will be presented by visit.
- Mean plots for mean dose (mg/day), weight adjusted mean dose (mg/kg/day), cumulative dose (mg) and weight adjusted cumulative dose (mg/kg).

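### The protocol sets out to show faster-than-usual steroid tapering, but the single-arm plan has no reference time and no time-to-taper endpoint, and its one taper threshold does not separate a fast taper from a slow one

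*Protocol*

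**What the plan says.** Protocol 1.3 (Study Rationale) gives the design aim as demonstrating that "successful tapering of corticosteroids over a shorter period of time than physicians have been accustomed to will be possible with the administration of bertilimumab". Protocol 1.3 and SAP 1.1 add that efficacy in newly diagnosed patients would be proven by lower initial doses and a lower cumulative dose, achieved by "facilitating rapid tapering to 10 mg prednisone equivalent or lower after initial control of BP lesions".

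The endpoint in protocol 2.2 is "Proportion of patients who have tapered to prednisone dose of ≤10 mg/day at Visit 8 (Day 84) and/or 2 and 4 months after Visit 8". SAP 7.2.1 (Prednisone Dose) keeps only the first time point and scores a success "if the dose at Visit 8 (Day 84) does not exceed 10 mg/day". SAP 9.4.1 then states: "Frequency distribution of dichotomous reduction in mean dose will be presented by visit".

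Table 1 (protocol 6.8.1) is a recommended schedule. Above 10 mg/day it reads "Decrease by 5 mg each week"; from 10 mg/day down it reads "Decrease by 2.5 mg each week".

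SAP 7.2.1 and 9.4.1 also plan mean dose, cumulative dose and reduction from Visit 2, by visit. The only time endpoint in protocol 2.2 is time to control of disease activity.

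**The concern.** The aim in protocol 1.3 concerns how long tapering takes. To support it, a plan needs a measured tapering time and something to compare it with, and this plan has neither: it gives no usual tapering time, no limit for what counts as rapid, no control arm and no time-to-10-mg variable. The one pass/fail result is a status on a late date, so patients who reach 10 mg/day on Day 28 and on Day 84 are scored alike.

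The rule also requires no reduction. Newly diagnosed patients may enter on less than 30 mg/day with no stated minimum, so someone at or below 10 mg/day on Day 0 who stays there is a success.

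The results are intended for internal decisions on further development. A Day 84 proportion quoted beside the stated aim could carry more weight than it can bear.

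**Working it through.** The documents give no expected tapering time, so there is no planned figure to reproduce. The check asks how slow a taper can be and still meet the threshold.

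**Inputs.** Steps of 5 mg above 10 mg/day and 2.5 mg from 10 mg/day down, weekly (Table 1). Day 0 dose of 30 mg/day for newly diagnosed patients who had been on 30 to 40 mg/day, and a stable lower dose for the others (protocol 6.8.1). Threshold ≤10 mg/day at Day 84; later calls at about Days 144 and 204; visit window ±2 days (protocol Appendix A).

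**Assumptions.** The first cut comes one interval after Day 0; the variant has it on Day 0. For taper-resistant patients no upper starting dose is stated, so values above 30 mg/day are illustrative.

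**Formula.** With a step every 7k weeks-in-days (k = 1 is Table 1), days to 10 mg/day = 7k × (start − 10)/5. Largest slowdown that still passes = 84 / (days on Table 1).

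| Day 0 dose (mg/day) | Table 1 reaches 10 mg/day | Three times slower | Largest slowdown passing at Day 84 |
|---|---|---|---|
| 20 | Day 14 | Day 42 | 6.0 |
| 25 | Day 21 | Day 63 | 4.0 |
| 30 | Day 28 | Day 84 | 3.0 |
| 35 | Day 35 | Day 105 | 2.4 |
| 40 | Day 42 | Day 126 | 2.0 |
| 50 | Day 56 | Day 168 | 1.5 |

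With the first cut on Day 0, a 30 mg/day start reaches 10 mg/day on Day 21 and the margin is 84/21 = 4.0.

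**Cumulative dose from 30 mg/day, Days 0 to 83.**
- Table 1: 7 × (30 + 25 + 20 + 15 + 10 + 7.5 + 5 + 2.5) = 7 × 115 = 805 mg.
- One third of the speed: 21 × (30 + 25 + 20 + 15) = 21 × 90 = 1,890 mg.
- Ratio 1,890/805 = 2.3. Both patients are at or below 10 mg/day on Day 84 and score 1.

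**Boundary.** The threefold case at 30 mg/day passes with equality. If Visit 8 falls on Day 82 the dose is still 15 mg/day and the patient fails; on Day 84 or 86 it is 10 mg/day and the patient passes.

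**Later time points in the protocol.** If either call can satisfy the endpoint, the margin from 30 mg/day grows to 144/28 = 5.1 and 204/28 = 7.3.

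**What the other summaries would show.** For the same two patients, mean dose over Days 28 to 41 is (10 + 7.5)/2 = 8.75 mg/day on Table 1 and 25 mg/day on the slow taper.

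**The case against.** The strongest reply is that the plan as a whole does not lose the timing; only the Day 84 indicator does. SAP 7.2.1 says mean and cumulative dose are both of interest and derives them per patient and period. SAP 9.3.2 lists each patient's corticosteroid doses with start and end dates, and the protocol synopsis promises patient narratives. With at most 15 patients, a reader could work out each time to 10 mg/day by hand. In the rationale shared by protocol 1.3 and SAP 1.1, lower cumulative dose is itself a named outcome, and it is summarised. This stands: it would be wrong to infer that a slow taper would go unseen. What remains is that no planned summary states the time, and none has a reference value.

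A reader might also infer that a high Day 84 proportion would formally count as proof of rapid tapering. The documents do not support that. The secondary objective is preliminary evidence, the analysis is descriptive, no decision rule uses the proportion, and protocol 1.3 leaves demonstration to later randomised trials. The overstatement sits in the rationale wording.

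Finally, a time variable added now is late: SAP 7.4 refers to a decision taken after the study was completed. Comparing patients with Table 1 would show adherence to the trial's own schedule, not tapering faster than usual. Both points are accepted and shape the fix.

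**Conclusion.** The point holds in a limited form. The stated aim of showing shorter-than-accustomed tapering cannot be met by a single-arm study with no reference time, and the plan does not summarise the tapering time it could describe. The threshold is weak as a measure of speed: from 30 mg/day it tolerates a taper up to three times slower than Table 1.

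It would be too strong to say that a threefold slower taper always passes. That figure rests on a 30 mg/day start, a first cut after one interval and Visit 8 no earlier than Day 84. It also takes the Visit 8 dose as the dose on that day or the mean from that day onward; SAP 7.2.1 gives no end for the Visit 8 period. The margin widens below 30 mg/day and shrinks above it, where taper-resistant patients may start.

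It would also be wrong to call Day 84 the only time point. That is true of the SAP but not of the protocol, whose later calls loosen the criterion. The primary safety objective is unaffected.

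**What to change.** 1. In SAP 7.2.1 and 9.4.1, add a descriptive per-patient time from Day 0 to the first day at ≤10 mg/day prednisone equivalent that is then maintained through Visit 8. Take it from the dated steroid records, censor at the last record, and give the Kaplan-Meier median and the individual times. Include only patients above 10 mg/day on Day 0, report how many are excluded, and label the variable as added after study completion.
2. Define the ≤10 mg/day indicator at every visit, so that SAP 7.2.1 matches the by-visit display in 9.4.1, and report it also among patients above 10 mg/day on Day 0. Reconcile the SAP with protocol 2.2 on the two later calls, and state the period behind the Visit 8 dose.
3. In SAP 1.1 and the study report (and protocol 1.3 if it is amended), replace the language of demonstration and proof with a description of time to ≤10 mg/day and cumulative dose as preliminary evidence. Label any display against Table 1 as adherence to the recommended schedule.

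The cost is one derived variable, one table or figure and some rewording, with no new data, visits or patients. The price is a more modest conclusion and a wide interval around the median with at most 15 patients.
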